#### **4.5. Study Days and Visits**

Study days are numbered relative to the first day of study drug administration. The start of treatment (Day 1) is defined as the date on which a patient takes the first dose of study drug, as recorded on the study drug diary. Days will be numbered relative to treatment start (ie, ..., -2, -1, 1, 2, ...; with day 1 being the first day of study drug administration and day -1 being the day before the first day of study drug administration).

For efficacy and safety by-visit analyses, data collected at postbaseline scheduled visits will be included using their scheduled visit, data collected at postbaseline unscheduled visits will be included and assigned to their corresponding scheduled visit, and data collected at early termination visits will be included and assigned to the next scheduled visit. After the assignments are made, if there is a scheduled and unscheduled visit at the same visit, the scheduled visit will be used in the analysis.

## **5. STUDY POPULATION**

### **5.1. General**

The ITT analysis set will be used for all study population summaries. Summaries will be presented for all patients.

### **5.2. Patient Disposition**

Patient screened, patients screened but not in the ITT analysis set (and reason not in the ITT analysis set) will be summarized using patient counts. Patients in the ITT analysis set, patients in the ITT analysis set but not treated, patients in the safety and full analysis sets, patients who completed treatment and completed study, and patients who withdraw from the treatment and study (and reasons for withdrawing) will be summarized using descriptive statistics.

### **5.3. Demographics and Baseline Characteristics**

For demographics, the continuous variables of patient age, weight, height, and body mass index (BMI) will be summarized using descriptive statistics. The categorical variables of patient sex, race, and ethnicity will be summarized using descriptive statistics for each category. Missing categories will be presented if necessary.

For baseline characteristics, the categorical variables of CYP2D6 metabolizer genotype (poor, extensive, intermediate or ultra-rapid metabolizer), neuroleptic use, and number of Cytosine-Adenosine-Guanine (CAG) repeats, all determined from baseline in the PRIDE-HD or HART studies, will be summarized using descriptive statistics for each category. Missing categories will be presented if necessary.

For socio-economics, the continuous variables of year of education, years in occupation most of career, years in current occupation, and number of times married will be summarized using descriptive statistics. The categorical variables of occupation most of career, current occupation, marital status, and handedness will be summarized using descriptive statistics for each category. Missing categories will be presented if necessary.

### **5.4. Medical History**

All medical history will be coded using the Medical Dictionary for Regulatory Activities (MedDRA). The incidence of medical history abnormalities will be summarized using descriptive statistics by system organ class (SOC) and preferred term (PT). Patients are counted only once in each SOC category, and only once in each PT category.

### **5.5. Prior Therapy and Medication**

Any prior therapy or medication a patient has had prior to screening will be recorded on the case report form (CRF). The sponsor will encode all therapy and medication according to the World Health Organization (WHO) drug dictionary (WHO Drug).

The incidence of prior therapies and medications will be summarized using descriptive statistics by therapeutic class and PT. Patients are counted only once in each therapeutic class category,

and only once in each PT category. Prior therapies and medications will include all medications taken and therapies administered before the first day of study drug administration.

### **5.6. Electrocardiography**

ECG findings (normal and abnormal) at baseline will be summarized using descriptive statistics.

### **5.7. Physical Examinations**

Physical examination abnormal findings at baseline will be summarized using descriptive statistics.

### **5.8. Study Protocol Violations**

Data from patients with any protocol violations (as recorded in protocol violation CRF) during the study will be summarized overall and for each category using descriptive statistics.

## **6. EFFICACY ANALYSIS**

### **6.1. General**

The full analysis set analysis set will be used for all study population summaries unless otherwise noted. Summaries will be presented for all patients.

### **6.2. Efficacy Endpoint and Analysis**

The efficacy endpoints are as follows:

- UHDRS-TMS change from baseline to each visit that this is measured.
- UHDRS-TFC change from baseline to each visit that this is measured.
- UHDRS-FA change from baseline to each visit that this is measured.
- UHDRS-IS change from baseline to each visit that this is measured.
- UHDRS Behavioral total score change from baseline to each visit that this is measured.
- UHDRS Cognitive tests change from baseline to each visit that this is measured.
- PBA-s total score change from baseline to each visit that this is measured.

All efficacy endpoints will be summarized for actual values and changes from baseline to each visit using descriptive statistics.

UHDRS Behavioral domain scores and the PBA-s domain scores will also be summarized for actual values and changes from baseline of this study to each visit using descriptive statistics.

No formal inferential statistics will be applied to the efficacy endpoints. Efficacy analyses will be considered exploratory.

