## **8.3 Missing Values**

Missing values will not be imputed.

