## **1. STUDY OBJECTIVES**

The objective is to assess the long-term safety of pridopidine and to analyze treatment effects during long-term, open-label treatment.

The primary objective of this study is to evaluate the long-term safety of pridopidine treatment and to collect information on Unified Huntington's Disease Rating Scale (UHDRS) development during long-term, open-label treatment.

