#### **Withdrawal from treatment**

If the patient wishes to stop the drug, or is judged by the investigator to not be suitable for continued therapy, or the study is discontinued, a clinic visit ("withdrawal visit", end of study drug visit) should be performed and the patient withdrawn from the study. A (telephone) follow-up visit (30 d TC F/U) to collect and report AEs (as well as inquiry about changes in use of benzodiazepines and antidepressants, and inquiry about changes in use of alcohol and illicit drugs), C-SSRS and an abbreviated PBA-s assessment should take place one month after the actual discontinuation of study drug took place.

Patients who discontinue study medication due to safety or tolerability reasons may continue in the study off drug and perform the scheduled visits and assessments.

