### **4.4. Handling Withdrawals and Missing Data**

For all variables, only the observed data from the patients will be used in the statistical analyses, ie, there is no plan to estimate missing data.

For the TMS component of the UHDRS, if responses to 1 assessment up to 25% of assessments are missing, the missing responses will be replaced by the average of the remaining responses within the TMS component. If responses to more than 25% of the assessments are missing, the missing responses will not be replaced and the UHDRS-TMS will be set to missing.

For the TFC scale of the UHDRS, if responses to 1 item up to 25% of items are missing, the missing responses will be replaced by the average of the remaining responses within the TFC scale. If responses to more than 25% of the assessments are missing, the missing responses will not be replaced and the UHDRS-TFC will be set to missing.

For the FA component of the UHDRS, if responses to 1 assessment up to 25% of assessments are missing, the missing responses will be replaced by the average of the remaining responses within the FA component. If responses to more than 25% of the assessments are missing, the missing responses will not be replaced and the UHDRS-FA will be set to missing.

For the behavioral assessment of the UHDRS and the PBA-s, the severity x frequency items need to be calculated before calculating the total score. If either the severity or frequency value is missing then the item will be equal to the nonmissing value. After calculating the items, if responses to 1 item up to 25% of items are missing, the missing responses will be replaced by the average of the remaining responses. If responses to more than 25% of the items are missing, the missing responses will not be replaced and the total score will be set to missing.

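### UHDRS course is described only by observed-case summaries at each yearly visit, which are likely to make progression look slower if patients who worsen leave more often

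*SAP*

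**What the plan says.** SAP section 1 gives as part of the primary objective to "collect information on Unified Huntington's Disease Rating Scale (UHDRS) development during long-term, open-label treatment".

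The analysis of that part is in SAP 6.2: "All efficacy endpoints will be summarized for actual values and changes from baseline to each visit using descriptive statistics". The same section adds: "No formal inferential statistics will be applied to the efficacy endpoints". It calls the efficacy analyses exploratory.

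On missing data, SAP 4.4 says: "For all variables, only the observed data from the patients will be used in the statistical analyses". Its replacement rules cover missing items within a form (up to 25%), not missed visits. Protocol 8.3 agrees: "Missing values will not be imputed".

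Four other provisions bear on the point.
- UHDRS is done yearly (SAP 2.1), and the top exposure category is more than 6 years (SAP 7.2).
- Under SAP 2.1, if the patient wishes to stop or is "judged by the investigator to not be suitable for continued therapy, or the study is discontinued, a clinic visit" is held and the patient leaves the study. Patients who stop for safety or tolerability may stay on off drug, but need not.
- SAP 4.5 places data from an early-termination visit in the next scheduled visit.
- The full analysis set needs a baseline and at least one later motor score (SAP 3.1.3), so a patient who leaves before any repeat is never counted.

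Neither document plans a longitudinal model, a summary by time of leaving, or a sensitivity analysis for dropout.

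**The concern.** At each visit the mean change describes the patients who have a value there. Once a leaver's last value has been used, that patient is missing from every later mean. If leaving is related to how fast a patient worsens, the make-up of the later means shifts towards slower progressors. The year-5 or year-6 figure then describes those who stayed, while the table reads as the course on treatment.

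Such a link is plausible. The protocol background describes steady decline in Huntington's disease, and patients who wish to stop or are judged unsuitable are withdrawn. Any distortion grows with time, and the late part of the curve is what a long extension is there to describe. From the planned output a reader could not tell slow progression from selective loss.

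**Working it through.** **Plan's own figure.** There is none to reproduce. Neither document gives a dropout rate, a rate of progression or a variance. Every numeric input below is an assumption.

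**Model for the UHDRS Total Motor Score (TMS).**
- Change at year t: b·t + e(t) − e(0). The slope b has mean 3 and SD 2 points a year. The residual e has SD 4 at baseline and at each visit.
- Leaving between year t and t+1: logit P = logit(d) + log(OR) × (last observed change − 3t). Here d is 5%, 10% or 20% a year, and OR is 1.05 or 1.10 per point. In the first year P = d.
- SAP 4.5 rule: a leaver's final score is taken mid-interval and counted in the next yearly UHDRS visit. Reading the next scheduled visit in this way favours the plan.
- 400,000 simulated patients per scenario. The true change is 3 × 5 = 15 at year 5 and 3 × 6 = 18 at year 6.

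**How strong is that link?** At year 4 the SD of change is √((2×4)² + 4² + 4²) = √96 = 9.8 points. The odds ratio per SD is then 1.05^9.8 = 1.6 or 1.10^9.8 = 2.5.

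**Observed-case mean change at year 5, with the early-termination rule (true value 15.0).**

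| Yearly dropout | OR 1.05 | OR 1.10 |
|---|---|---|
| 5% | 14.5 (about 4% low) | 13.9 (about 7% low) |
| 10% | 14.0 (7% low) | 13.1 (13% low) |
| 20% | 13.0 (13% low) | 11.6 (23% low) |

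Percentages come from unrounded means. For example, 1 − 13.0/15 = 13% and 1 − 11.6/15 = 23%. At year 6 with 20% dropout the means are 14.8 and 12.5 against 18, or 18% and 30% low, so the gap widens.

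**Effect of the early-termination rule.** Without it, the year-5 means at 20% dropout are about 12.6 and 10.5 (16% and 30% low). The rule reduces the bias but does not remove it.

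**Second check with different settings.** True worsening was 1 unit a year, slope SD 0.6, residual SD 0.5, and OR 1.5 to 3 per SD of last observed change. The early-termination value was placed at the scheduled visit.
- For 5% to 20% yearly dropout, the shortfall is 4% to 36% at year 6 but only 1% to 10% at year 3.
- With OR 1 there is no bias.
- At 15% dropout with OR 0.67 or 0.5 (slower progressors leave more), the year-6 mean is 13% or 21% too high.

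**The alternative on the same kind of data.** A random-intercept-and-slope model gave 3.00 and 3.07 points a year against a true 3. This used the TMS settings at 20% dropout without the early-termination rule, in 12 replicates of 300 patients. Good recovery is expected here, because dropout was made to depend on observed change.

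**The case against.** **A stronger reading.** A reader might infer that the planned means do understate progression, and by a large amount. The documents do not support that. The SAP withdrawal text does not mention worsening. Protocol 7.7.2 does let the investigator stop drug for a worsening condition. However, that text is in the Amendment 05 protocol, which SAP 2.1 says was not implemented, and the Amendment 04 wording is not available. Patients also entered from two parent studies and the study may stop for commercial reasons, so some thinning of late visits may have nothing to do with outcome. Direction and size therefore both remain conditional.

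**Status of the analysis.** The objective is to collect information, efficacy is labelled exploratory, and there is no control arm, so a model slope would not isolate a drug effect. This lowers the consequence. It does not settle the point, because describing the UHDRS course is itself part of the primary objective.

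**Existing safeguards.** The tables show n at each visit, and withdrawals are tabulated with reasons. These show that patients left, not whether they were the ones worsening. Medians and graphs rest on the same remaining patients.

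**Limits of the model.** It assumes missing-at-random dropout and roughly linear change over six years. It may also be imprecise. The only patient number in the documents is 47, for the virtual phase that was not implemented. With 47 patients and slope SD 2, the standard error of the mean slope is at least 2/√47 = 0.29. The 95% CI is then at best about ±1.96 × 0.29 = ±0.57 points a year. This objection stands, and is a reason to print the interval and state the assumptions.

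**Conclusion.** The point holds in conditional form. The plan describes the UHDRS course by observed-case summaries alone, and a leaver's data support only one further visit. If worsening patients leave more often, later means are likely to understate progression.

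Under the TMS assumptions the year-5 shortfall runs from about 4% (5% yearly dropout, OR 1.05) to 23% (20% yearly dropout, OR 1.10). Dropout unrelated to change leaves the means essentially unbiased, and the opposite pattern reverses the sign. The documents establish the gap in the plan. They do not establish that bias occurred or how large it is. The addition is worth making because it is cheap and addresses a stated objective.

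**What to change.** Keep all planned tables. Add to SAP 6.2, for each UHDRS score, an exploratory linear mixed model:
- all observed values at their actual assessment times, including early-termination values, with baseline as an outcome;
- time in years, random intercept and random slope;
- the estimated yearly change with its 95% CI and no test;
- a label saying that the estimate is valid under missing-at-random dropout and approximate linearity.

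The sentence in SAP 6.2 that rules out formal inference needs a clause saying that the interval is for estimation only.

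Optionally, print beside each visit mean the baseline mean of the same patients. This gives context on who remains, but does not correct selection on slope, since change from baseline is already within patient.

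The cost is a short SAP paragraph and one model per score, with no new data. SAP 2.6.2 allows amendments to be approved up to database lock. The downside is reliance on the two labelled assumptions: dropout that depends on unobserved worsening would not be fully corrected.

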## **7. SAFETY ANALYSIS**

### **7.1. General**

The safety analysis set will be used for all study population summaries unless otherwise noted. Summaries will be presented for all patients.

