### 2.3 Rationale for Dosage Used

Patients entering this study were treated with either 0 (placebo), 10, 22.5 or 45 mg pridopidine bid in the HART study, or 0 (placebo), 45, 67.5, 90, or 112.5 mg pridopidine bid in the PRIDE-HD study.

The proposed dose selected for this study is pridopidine 45 mg bid. The proposed dose has been evaluated in 3 large HD clinical studies (HART, MermaiHD, and PRIDE-HD) as well as 2 open-label extension studies (Open-HART and Open-PRIDE-HD) and has been generally well tolerated. In PRIDE-HD, 45 mg bid was the lowest of 4 doses evaluated. [REDACTED]

[REDACTED] Thus, from a benefit-risk perspective, the Sponsor sees no benefit in continuing to explore doses higher than 45 mg bid. [REDACTED]

[REDACTED] Thus, the Sponsor sees no therapeutic benefit at exploring doses lower than 45 mg bid.

Both pharmacokinetic data and clear dose-dependent and exposure-dependent QTc findings in PRIDE-HD rule out systematic dosing errors. While the HART and MermaiHD studies had explored the clinical profile of doses up to 45 mg bid, PRIDE-HD was designed to test the high end of exposure on potential clinical benefit (Food and Drug Administration [FDA] Type C meeting; 24 July 2013).

The integrated safety analysis and large safety database from the double-blind, placebo-controlled HART, MermaiHD, and PRIDE-HD studies indicated that the AE profile of pridopidine 45 mg bid is generally well tolerated and comparable with placebo. [REDACTED]

The integrated analysis of data from the double-blind, placebo-controlled HART, MermaiHD, and PRIDE-HD studies indicated the following:

- [REDACTED]
- [REDACTED]
- [REDACTED]
- [REDACTED]
- [REDACTED]
- [REDACTED]

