#### 4.6 Conduct of the Study

The ACR16C015 (Open-HART) open-label extension study began in 2011 and has been ongoing in the United States and Canada (see [Appendix 1](#)) to evaluate the long-term safety and tolerability of pridopidine administered at a dose of 45 mg bid in adult patients with HD

who completed the treatment period of the HART or PRIDE-HD studies. The primary reason for this amendment is to evaluate the feasibility of virtual study conduct and remote assessments administered in adult patients with HD receiving pridopidine 45 mg bid. All clinical sites will conduct study assessments remotely. The study will consist of a VTV, an open-label treatment period, and a follow-up period (30 days after end of treatment). The study will continue under the same study number; however, all patients will have to be re-consented regardless of their current study status. A CRO will provide oversight and many functions will be performed centrally. The study will include both remote visits and safety telephone contacts (TC). Remote visits will be considered "virtual" visits and will be conducted by investigators (or qualified designees) via real-time video conferencing. Other procedures will be performed by qualified nurses who will visit the patients' homes (and/or applicable locations).

If patients have concerns about the virtual nature of the site visits, they may request an unscheduled visit (USV) at the investigational center. The medical monitor will review individual requests and may approve 1 site USV per patient, per year. The assessments at site USVs will mirror those obtained during safety evaluation TCs (see Section 4.6.4). The investigator (or qualified designee) may schedule additional site visits on a case-by-case basis for patients that require closer monitoring due to safety events.

Patients excluded from the study due to lack of internet connection or inability to transition from in-person study visits to virtual study visits may be eligible to enroll in the Open-PRIDE-HD study (Study TV7820-CNS-20016).

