## **8.8 Efficacy Set**

Descriptive statistics of each of the efficacy variables for the efficacy analysis set will be presented by yearly intervals. Changes in efficacy parameters will be calculated both from baseline (in main study) and from start of this extension part.

The efficacy parameters will also be presented graphically.

Efficacy data will be presented for all patients combined.

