At **Visit 1 (1 Month)** the following will be documented: an evaluation for research study consent, review of concomitant medications (including inquiry about changes in use of benzodiazepines and antidepressants); inquiry about changes in use of alcohol and illicit drugs, AEs, C-SSRS, PBA-s, vital signs and drug compliance. Evaluation for Research Study Consent, ECG and blood draw (calcium, magnesium, potassium, and creatinine for creatinine clearance calculation) will be performed for patients from the PRIDE-HD study.

Subsequently, the patient will be contacted every 3 months as per below:

At **Telephone or in-person Visits [Safety Visit (SV)] (eg after 3, 9, 15 months etc.)** the following will be documented: an evaluation for research study consent, review of concomitant medication (including inquiry about changes in use of benzodiazepines and antidepressants); inquiry about changes in use of alcohol and illicit drugs, C-SSRS and PBA-s assessment, review of AEs, and assessment of compliance with trial medication. A 12-lead ECG will be obtained, vital signs will be assessed and calcium, magnesium and potassium level and creatinine for

creatinine clearance calculation will be drawn [hypokalemia is defined as a potassium level less than 3.5 mEq/L]. If less than 3.5 mEq/L, patient's study drug will be suspended until normal (greater than or equal to 3.5mEq/L). Participants can choose to have the assessments of vital signs, ECG and blood draw for calcium, magnesium, potassium, and creatinine for creatinine clearance calculation performed by their GP and/or local cardiologist or schedule a visit with site but the site must have a telephone contact with the participant to review concomitant medication, AEs and assess compliance with trial medication.

At **Telephone contacts [C] (eg once a month between on-site visits)** the following will be documented: an evaluation for research study consent, review of concomitant medication (including inquiry about changes in use of benzodiazepines and antidepressants); inquiry about changes in use of alcohol and illicit drugs, review of adverse events, C-SSRS and an abbreviated PBA-s assessment.

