## **2.5. Sample Size and Power Considerations**

As this is an open-label extension study, no sample size calculations have been performed. Patients who completed the HART or the PRIDE-HD study and met patient exclusion/inclusion criteria will be enrolled.

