### 7.5. Electrocardiography

Shifts (normal and abnormal) from baseline to overall finding and each visit will be summarized using patient counts. For overall finding, the summary will use the worst postbaseline finding for the patient (the abnormal finding if there are both normal and abnormal findings). Summary statistics for ECG variables will be presented at baseline and each visit. Actual values and changes from baseline to each visit will be summarized using descriptive statistics.

The incidence of potentially clinically significant abnormal values for ECG variables will be summarized using descriptive statistics with the criterion specified below.

- QTcF values  $>450$  ms or  $>480$  ms or  $>500$  ms.
- QTcF change from baseline values  $>30$  or  $>60$ .
- PR change from baseline  $\geq 25\%$  and value  $>200$ .
- QRS change from baseline  $\geq 25\%$  and value  $>110$ .
- Heart rate value  $<60$  bpm or  $>100$  bpm.

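### Pooling HART and PRIDE-HD rollovers lets by-visit means move with cohort mix: the Month 1 ECG row is PRIDE-HD only and the latest visits can be HART only

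*SAP*

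**What the plan says.** **Who enters.** SAP 2.5: "Patients who completed the HART or the PRIDE-HD study and met patient exclusion/inclusion criteria will be enrolled". SAP 2.1 notes that the plan follows protocol Amendment 04 and that Amendment 05, the protocol text supplied, was not implemented.

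**Pooling.** SAP 5.1, 6.1 and 7.1 each state "Summaries will be presented for all patients". Protocol 8.8 takes the same line for efficacy: "Efficacy data will be presented for all patients combined". No SAP section splits results by parent study, and parent study is not among the baseline characteristics in SAP 5.3.

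**By-visit output.** SAP 6.2: "All efficacy endpoints will be summarized for actual values and changes from baseline to each visit using descriptive statistics". SAP 7.5, for ECG: "Actual values and changes from baseline to each visit will be summarized using descriptive statistics". SAP 7.4 does the same for vital signs, and SAP 7.3 adds a summary of AEs by period of treatment.

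**Who is measured at Month 1.** SAP 2.1 plans a baseline ECG for all patients. At Visit 1 (Month 1), "ECG and blood draw (calcium, magnesium, potassium, and creatinine for creatinine clearance calculation) will be performed for patients from the PRIDE-HD study". The later safety and clinic visits, from Month 3, plan an ECG with no limit by parent study.

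**When the cohorts entered.** Protocol 4.6: "The ACR16C015 (Open-HART) open-label extension study began in 2011 and has been ongoing". Protocol 2.3 ties the design of PRIDE-HD to an FDA meeting on 24 July 2013.

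**Prior dose.** Protocol 2.3: "Patients entering this study were treated with either 0 (placebo), 10, 22.5 or 45 mg pridopidine bid in the HART study". For PRIDE-HD the same sentence gives 0 to 112.5 mg bid.

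**The concern.** A pooled by-visit table reads as a time course only if roughly the same kinds of patient stand behind each row. Here the schedule and the calendar change the cohort mix at two places: at Month 1 for the ECG, and at the longest follow-up for every by-visit table. If the cohorts differ, a step in mean QTcF between Month 1 and Month 3, or a late bend in UHDRS, could come from who is in the row.

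This matters because long-term safety and UHDRS development are the primary objectives (SAP section 1) and the analysis is descriptive. No model or test stands behind the tables, so the printed time course is the result. The risk is a misread trend, not an inflated error rate.

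**Working it through.** The plan states no sample size, cohort sizes or expected QTcF difference, so there is no figure to reproduce. Two checks apply.

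**1. Calendar gap between cohorts.**
Inputs: extension start in 2011, month not given (Protocol 4.6); 24 July 2013 as a floor for any PRIDE-HD entry, since completers cannot roll over before the study's design was settled (Protocol 2.3). I assume that the first HART patients entered in 2011.

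- Latest 2011 start: 31 Dec 2011 to 24 July 2013 = 1.56 years.
- Earliest 2011 start: 1 Jan 2011 to 24 July 2013 = 2.56 years.

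The gap is therefore at least about 1.6 to 2.6 years, with nothing added for the PRIDE-HD treatment period. If PRIDE-HD entry opened only with Amendment 03 (2 February 2015, an assumption), it is 3.1 to 4.1 years.

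Longest possible follow-up in years, for assumed cut-offs and the 2013 floor:

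| Assumed cut-off | HART | PRIDE-HD, at most |
|---|---|---|
| 29 June 2017 | 5.5 to 6.5 | 3.9 |
| 29 June 2018 | 6.5 to 7.5 | 4.9 |
| 29 June 2019 | 7.5 to 8.5 | 5.9 |

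A HART-only end to the longest follow-up exists at any cut-off; where it starts depends on dates not given. The top exposure class in SAP 7.2, above 6 years, can hold only HART patients if the cut-off is before 24 July 2019.

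**2. Effect of a changing mix.**
Let w be the HART share, and let d be the HART mean minus the PRIDE-HD mean, held constant so that nobody changes.

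- Mixed row: w × HART mean + (1 − w) × PRIDE-HD mean.
- PRIDE-HD-only row (Month 1 ECG) minus mixed row: −w × d.
- HART-only row (latest visits) minus mixed row: +(1 − w) × d.

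Size of the Month 1 shift, w × d, in ms; w and d are both assumed:

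| w | d = 2 | d = 5 | d = 10 |
|---|---|---|---|
| 0.2 | 0.4 | 1.0 | 2.0 |
| 0.5 | 1.0 | 2.5 | 5.0 |
| 0.8 | 1.6 | 4.0 | 8.0 |

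The late shift, (1 − w) × d, covers the same 0.4 to 8 ms with the rows in reverse order and the opposite sign relative to the mixed rows.

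**3. What d means for each kind of row.** In actual-value rows, d is any difference in level. In change-from-baseline rows a constant level difference cancels within each patient, so d must be a difference in mean change. Such a difference is possible but not quantified. SAP 4.2 takes baseline before the first dose in this extension, prior doses ran to 45 mg bid in HART and 112.5 mg bid in PRIDE-HD, and Protocol 2.3 reports QTc findings in PRIDE-HD that depended on dose and exposure. Any carry-over from the parent study would alter both baseline and change.

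**The case against.** The strongest reply is that this is narrow and partly visible already.

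- **Scope.** A reader might infer that every pooled line starts as PRIDE-HD only. The documents do not support that. Month 1 vital signs are taken in all patients, UHDRS is done at baseline and yearly, and the ECG series begins with a baseline planned for everyone. Only the Month 1 ECG row is affected at the early end. This stands.
- **Dates.** A reader might infer a proven gap of two years or more, or a bend at year 3 or 4. The documents give no first PRIDE-HD entry date, treatment length or cut-off, so only the lower bound above and an unlocated HART-only end are supported. This stands.
- **Change scores.** Constant level differences cancel in the listed efficacy endpoints, which are changes. This stands for those rows, not for the actual values that SAP 6.2 and 7.5 also print.
- **Patient-level ECG output.** QTcF threshold counts, counts of large changes and worst-finding shifts do not rest on comparing visit means. They are largely unaffected.
- **Visibility.** SAP 4.1 prints n, so the Month 1 drop and the late thinning will show. But n alone does not say which cohort is missing.
- **Unscheduled ECGs.** SAP 4.5 could map an unscheduled HART ECG to Month 1. Such patients would be few and selected, so this does not repair the row.
- **Stated choice.** Pooling is deliberate, and Protocol 8.9.2 sends combined HART and Open-HART AEs to an integrated safety summary. Neither supplies the by-visit split.
- **Small cells.** The only patient count given is 47, in the synopsis of the unimplemented amendment; the SAP population may differ. This counts against splitting every AE table or showing first-year AEs by prior assignment.

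The pre-virtualization schedule in Protocol 1.2 is not in the text available, so the Month 1 rule rests on SAP 2.1 alone.

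**Conclusion.** The concern holds in limited form. The ECG restriction at Month 1 is explicit in the SAP. The HART-only end of follow-up is an inference, but it needs only the 2011 start, the 2013 date and HART entry in 2011. Neither place is marked in the pooled tables.

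The size cannot be determined from the documents. The 0.4 to 8 ms range rests on an assumed share and an assumed gap and shows what is possible, not what is expected. It applies to actual values for any level gap, and to changes only if change differs by cohort. A reader might infer that the ECG safety conclusions as a whole are compromised; they are not, because the patient-level summaries do not depend on the visit means. The exposure is to misreading the by-visit trends and the AE-by-period summary.

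**What to change.** In SAP 6.1 and 7.1:

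- Present the by-visit UHDRS, ECG and vital-sign tables by parent study (HART, PRIDE-HD) as well as overall, with n by parent study at each visit.
- Label the Month 1 ECG row as PRIDE-HD only, and state that it is not to be read as part of the pooled trend.
- Show the AE-by-time-period summary already planned in SAP 7.3 by parent study.

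The remaining AE tables can stay pooled. No new data are needed: SAP 5.3 already draws on parent-study baseline records. The cost is extra columns and some small cells. The split does not remove the effect of dropout within each cohort, so late visits will still need cautious reading.
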